11.0 Statistical/Data Analysis Plan

11.1 Statistical Considerations:

List the statistical methods to be used to address the primary and secondary objectives, specific aims, and/or research hypotheses. Explain how missing data and outliers will be handled in the analysis. The analysis plan should be consistent with the study objectives. Include any sub-group analyses (e.g., gender or age group). Specify statistical methods and variables for each analysis. Describe how confounding variables will be controlled in the data analysis

This is an interventional and discovery-based protocol that will identify associations between molecular and demographic information and clinical outcomes.

Descriptive statistics will report location and scale in terms of mean and standard deviation for normally distributed variables, median and interquartile intervals for ordinal metric variables, and in terms of proportion and size for categorical variables. Descriptive statistics will be reported for baseline demographic and clinical characteristics at an overall level and by initial treatment group.

Outliers will be removed if determined to be erroneous based on relevant clinical expertise. Confounding will be principally controlled by randomization. In regards to the treatment of

missing data, subjects with missing baseline or 6-week follow-up data will be excluded from Aim 1 analyses regarding change from baseline to six weeks but will be included in Aim 2 analyses across all relevant time points.

Statistical methods

For categorical variables, statistical methods may include tests such as the Fisher's exact test, Chi-square test, McNemar's test, or binomial test. For ordinal variables that do not approximate a continuous variable, tests such as ordinal logistic regression will be performed. For ranked data, tests such as Friedman's test will be used. For continuous random variables (ratio or interval types) or ordinal data that approximates a continuous random variable (e.g., Likert scale), t-tests will be used. The Wilcoxon signed rank test or Wilcoxon rank sum test will be used if the assumptions for the t-test do not hold. The normality assumption may be evaluated with a test that is appropriate given the sample size, objective, and intended audience, e.g., Shapiro-Wilk test, Jarque-Bera test, Kolmogorov-Smirnov test, or Anderson-Darling test. For analyses with more than two groups in the single independent variable or for analyses with more than one independent variable, single or multi-way ANOVAs will be performed, respectively. If a continuous variable is a potential covariate, then an ANCOVA will be performed. Post hoc tests will include tests such as Tukey's, Dunn's, Dunnett's, or pairwise univariate tests with false discovery rate correction, depending on the objectives of the analysis. Sequencing data will be analyzed using techniques that include negative binomial regression, PERMANOVA, and ANOSIM. Clustering will be performed using techniques such as hierarchical, k-means, k-medoids, Gaussian mixture models. These methods will attempt to minimize (or maximize depending on the metric) an error metric such as silhouette score, Akaike Information Criterion, or Bayesian Information Criterion with the specific metric being selected based on the best practice in the field, e.g., silhouette score for k-means. Clustering may be performed with or without first performing dimensionality reduction using Principal Components Analysis, Non-metric Multi-Dimensional Scaling, t-SNE, U-MAP, or another similar technique, depending on the data types, number of variables, and objectives. When analytic methods are unavailable, bootstrapping may be performed to estimate uncertainties, e.g. confidence intervals. Alternatively, if Bayesian methods are applied, then credible intervals will be calculated. When decision trees and decision-tree based methods (e.g., random forest, decision jungles) are used, feature importance may be calculated. When developing predictive models, both simple, explainable models (e.g., linear and logistic regressions) will be used when possible. When incorporating larger numbers of variables, neural network based models may be used. When such methods are applied, the optimum number of layers, dropout, activation functions, nodes, and other elements of model architecture will be determined empirically. Data will be split into training, cross validation, and testing groups in accordance with best practices in the machine learning and artificial intelligence fields. Regarding correlation analyses, correlations will be identified via methods that include Pearson's, Spearman's, and Kendall's tau. The specific method will be selected based on the bivariate distribution of the data, e.g. monotonic and linear vs. monotonic but not linear. Hoefding's D statistic may be calculated for non-monotonic relationships.

Missing data

Missing data will be handled as required by the statistical methods used:

1. For most analyses this means excluding the observations for which a relevant value is missing.
2. For some analyses, such as decision trees, missing values will be grouped together to create a new category.

Outliers

Outliers will be handled using a method appropriate for the statistical method used. For example, they may be excluded for parametric methods, however, they may be included when using non-parametric methods. If a non-parametric method cannot be used (e.g., none exist or they are not sufficiently interpretable), then the outlier may be excluded or replaced with a more appropriate value (e.g., a randomly selected value, the median, or one determined via an imputation method such as Multiple Imputation by Chained Equations). Results with and without the outlier will be compared to determine whether its exclusion impacts conclusions.

Sub-group analyses

Sub-group analyses will be performed for variables for which there is existing evidence (e.g., in the literature) or reason to suspect that they differ between groups. Such analyses may be performed as separate analyses (e.g., one analyses per group) or via incorporation of the grouping variable into the statistical model as in linear or logistic regression.

Handling confounding variables

When possible, confounding variables will be incorporated into models to control for their effects, e.g., in logistic regression. Whether confounders are included exclusively as direct effects or as direct effects plus interaction terms depends on the clinical nature of the variable. The most appropriate method of inclusion will be determined via discussions between medical staff and a statistician and/or bioinformatics analyst.

11.2 Sample Size:

Assuming attrition and accounting for screen failures, we are requesting to enroll up to 200 (50 per arm) participants in order to evaluate a final sample of 92 (30-31 per arm).

11.3 Total number of subjects requested (including records and specimens):

200

11.4 If you are recruiting by study arm, please identify the arms of the study and how many subjects will be enrolled in each arm

Up to 200 participants will be randomized 1:1:1:1 to the four treatment arms.

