11.5 Please provide a justification for your sample size

Since this is a discovery-based study of a novel topic, limited data are available with which to perform a power analysis. Thus we used a G*Power for a general comparison analysis without needing to root firmly in one specific variable.

If we are able to enroll 150 participants (a minimum of 92 post-attrition), assuming an effect size of .2, we will achieve 90% power. Effect size assumptions were taken from Tomazoni et al. 2016 based on the comparison of control versus PBMT with regards to biomarkers of gene expression that we assume to be an acceptable proxy for our primary comparison with regards to our biomarkers of concern. Significance threshold for power calculations was considered to be .01 to account for false discovery rate within our set of primary biomarker outcomes. Power calculations were performed using the WebPower package and the R Programming language.

11.6 Data Analysis Plan: Complete description: Background, Objectives, Design, Step by Step how the project is going to be done, Data analysis plan:

Aim 1 will be evaluated by comparing the PRP only and the PRP + PBMT treatment arms at six weeks relative to baseline. Generalized additive models predicting the fractional change in outcome measure at 6 weeks will be used.

Aim 2 will compare across all four treatment arms and will use Multi-Level models comparing the three treatment arms across time points and including random effects.

Aim 1 will include biomarker measures only; Secondary Aim 2 will include both biomarker measures and self-reports.

Hypothesis tests will be two-tailed and statistical significance will be considered at the putative threshold ($\alpha=0.05$). Any secondary P-values will be subject to a false discovery rate adjustment in keeping with best statistical practices. Multilevel models will incorporate random effects to account for repeated measures, using distribution families and link functions appropriate for the outcomes of interest, determined using QQ plots analyzed for best model fit. All statistical analyses will be performed using the R Programming language.

Clinical outcomes (pain scores) will be evaluated via ANOVA and post-hoc tests (Tukey's HSD test). A non-parametric alternative will be used if assumptions are not met.

Molecular Analyses:

DNA/RNA Analyses

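### Aim 1 is planned as a complete-case model of fractional change with no baseline term stated, which costs precision and can bias the PRP+PBMT versus PRP contrast if loss depends on baseline differently by arm

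*Combined protocol and SAP*

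**What the plan says.** Section 11.1 sets two missing-data rules. For Aim 1, "subjects with missing baseline or 6-week follow-up data will be excluded from Aim 1 analyses regarding change from baseline to six weeks". The same people are not dropped from Aim 2: "but will be included in Aim 2 analyses across all relevant time points".

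Section 11.6 defines the analyses. "Aim 1 will be evaluated by comparing the PRP only and the PRP + PBMT treatment arms at six weeks relative to baseline". The model is given in one sentence: "Generalized additive models predicting the fractional change in outcome measure at 6 weeks will be used". No baseline covariate is named. For the other aim, "Aim 2 will compare across all four treatment arms and will use Multi-Level models", although the same sentence goes on to refer to three arms. On outcomes, "Aim 1 will include biomarker measures only; Secondary Aim 2 will include both biomarker measures and self-reports". Aim 1 is therefore the lead aim by implication, and both aims cover biomarkers in the PRP and PRP+PBMT arms.

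Section 10.1 schedules blood and synovial sampling at baseline and at 6 weeks only. The size of the expected loss comes from section 11.5: "If we are able to enroll 150 participants (a minimum of 92 post-attrition". No sensitivity analysis for missing data is planned. Multiple imputation appears in section 11.1 only as a way to replace outliers.

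**The concern.** A change score subtracts the whole baseline value, whatever the correlation between baseline and week 6. That has two consequences. It is noisier than an analysis that uses baseline as a covariate. It also carries regression to the mean into the arm comparison whenever the completers in the two arms differ in mean baseline.

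Randomisation balances baseline among everyone randomised, but not among those who remain. The design leaves room for arm-specific loss. The PRP+PBMT arm has 3 x 3 = 9 laser sessions and the PRP arm has none. No sham is described. A participant who misses an appointment and is not reached in three attempts is removed (section 10.1), and no data are collected after withdrawal (section 13.6). If those removed from one arm tend to have higher or lower baseline marker levels, the comparison of changes can show a difference that treatment did not cause.

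**Working it through.** **The plan's own figure.** 150 - 92 = 58, and 58/150 = 38.7%. Applied to 50 per arm this leaves 50 x 0.613 = 30.7, in line with the 30-31 per arm in section 11.2.

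**Assumptions, not in the documents.** Standard deviation 1 at both times; correlation rho = 0.5; 50 per arm; about 39% week-6 loss; normal scale; two-sided 5% test; a t test on change in place of the planned generalized additive model.

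**Bias.** Given baseline Y0, the expected change is a constant minus (1 - rho) x (Y0 - mean). Among completers the expected difference in change is therefore

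true effect - (1 - rho) x D,

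where D is the arm difference in the completers' mean baseline. If loss depends on baseline equally in both arms, D = 0 and there is no bias. At rho = 0.5, a bias of 0.14 SD corresponds to D of 0.14/0.5 = 0.28 SD in size. Adjusting for Y0 removes the term.

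Simulation with no true effect and loss depending on baseline at 0.5-0.8 log-odds per SD:

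| Loss mechanism | Unadjusted change: bias (SD) | False positives | Adjusted, same completers |
|---|---|---|---|
| Random | 0.0 | 5% | bias about 0, 5% |
| Baseline-dependent, equal in both arms | 0.0 | 5% | bias about 0, 5% |
| Baseline-dependent, one arm only (at 0.8) | 0.14 | 8-9% | bias about 0, 5% |
| Baseline-dependent, opposite directions | 0.19-0.29 | 11-20% | bias about 0, 5% |

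At 0.5 log-odds in one arm only, bias is 0.10 SD and false positives 6-7%. Fractional change on log-normal data (log SD 0.6, t test) behaves similarly: about 8% false positives for one-arm dependence and 13% for opposite directions, against 5% with random loss.

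**Loss driven by the unseen week-6 value, one arm only.** Bias was -0.16 SD for unadjusted change, and -0.25 to -0.26 SD for adjusted complete cases and for the mixed models.

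**Precision.** The variance of change is 2(1 - rho); the residual variance after baseline adjustment is 1 - rho^2. The ratio is (1 + rho)/2, which is 0.65, 0.75 and 0.85 at rho = 0.3, 0.5 and 0.7.

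An arm-by-time mixed model without a baseline constraint, keeping baseline-only participants, has variance ratio [(1 + rho) + (1 - rho) m/n]/2, with n randomised and m complete per arm. At n = 50, m = 31, rho = 0.5 this is (1.5 + 0.5 x 0.62)/2 = 0.905, a 9.5% reduction. Across m = 23-31, n = 37.5-50 and rho = 0.3-0.7 the reduction is 3-19%. That is less than the gain from baseline adjustment alone.

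**Power.** Assume random loss of 30% at week 6 and 10% at baseline, and a true effect of 0.5 SD. Complete cases per arm: 50 x 0.7 x 0.9 = 31.5. The standard error of the difference in change is sqrt(2/31.5) = 0.252, so z = 0.5/0.252 = 1.98. With adjustment it is 0.252 x sqrt(0.75) = 0.218, so z = 2.29. The normal approximation gives power of 51% and 63%. Simulation with t tests, which is the better guide at this size, gives:

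- unadjusted change, complete cases: 49%
- baseline-adjusted, same complete cases: 60%
- baseline-adjusted, also keeping week-6 values with no baseline: 63%

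Adjustment therefore adds about 11 points and retention about 3.

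**The case against.** A reader might infer that discarding participants is the main harm, and that Aim 2 already holds a ready and better answer to the same question. The documents and the arithmetic do not support that.

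- **Retention is the smaller part.** With biomarkers sampled only twice, a baseline-only participant has no week-6 value to contribute. Adjusting the same complete cases removes all the simulated bias and recovers most of the power.
- **Aim 2 is not a finished substitute.** Section 11.6 specifies neither a baseline constraint nor a PRP+PBMT minus PRP contrast, and refers to both four and three arms. The proteomic text there omits missing data for primary and secondary outcomes, so retention is not assured for every marker.
- **Bias is conditional.** Loss must depend on baseline differently by arm, and the documents do not show that it will. If loss depends on the unseen week-6 value, models using baseline can do worse.
- **The 38.7% is not established loss among randomised participants.** The 92 is a stated minimum, so this attrition is already budgeted for power. X-ray and pregnancy screening follow consent and precede randomisation, section 11.2 says the enrolment request allows for screen failures, and no split is given. The 10% missing-baseline rate is an assumption; dry taps are lavaged and re-aspirated.
- **Aim 1 is primary only by implication.** The IRB approval memorandum gives a four-arm primary objective, and the protocol calls itself discovery-based.
- **Adjustment is not excluded.** Section 11.1 allows ANCOVA and adding confounders to models.

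These points stand and limit the claim. The last does not answer it: a general permission does not say whether the Aim 1 model includes baseline, so the choice would remain open until the data are seen.

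**Conclusion.** The point holds in a limited form. As written, Aim 1 is a complete-case analysis of fractional change with no baseline term stated. The main weakness is the unadjusted change score; excluding incomplete participants adds a little to it.

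At a correlation of 0.5, lack of adjustment costs about 11 points of power under the assumed random loss. It also leaves Aim 1 open to false positive rates of 8-9% or 11-20% under the two arm-dependent patterns above, and to no bias if loss is random or equally dependent on baseline. These sizes rest on the assumed correlation, loss rates and loss mechanisms, and on a t test; the planned additive model itself was not simulated. The remedy uses a baseline value that is already collected, so the change is worth making without proof that arm-dependent loss will occur.

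**What to change.** In sections 11.1 and 11.6:

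1. Estimate the Aim 1 contrast (PRP+PBMT minus PRP at week 6) with baseline adjustment, on a stated scale such as the log.
2. Preferably use a two-time-point mixed model in which baseline and week 6 are both outcomes, baseline means are constrained equal across arms, and every randomised participant with at least one value for that marker is included. Apply missingness per marker, not per participant.
3. Keep complete-case fractional change as a sensitivity analysis.
4. Report missingness by arm, and add a not-at-random sensitivity analysis, because the model in item 2 does not cure loss driven by unseen week-6 values.
5. Reconcile the Aim 2 arm count (four or three) and the proteomic omission rule with these choices.

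The cost is SAP wording and modest extra analysis. No new data or visits are needed.

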A self-report battery will be obtained using Appendix H Follow-Up Data Collection CRF, which will be administered at 3-weeks and 6-weeks post-intervention start.

A follow-up blood draw and synovial fluid aspiration will be completed at 6 weeks. The blood and synovial fluid samples will be processed by MAMC DCI staff as described in the "Sample Processing" section below.

Additionally, a chart review will be completed at 6 weeks to ensure that all related medical visit information is recorded in study documentation (Appendix I). A medical record review will be completed to obtain this information. A study visit is not required on behalf of the participant.

Participants will be evaluated for adverse events at each follow-up time point and any complications will be documented.

Data may be captured in person or remotely (e.g., entered directly into REDCap using a personalized coded link with no log-in required, verbally over the phone with a study team member, etc.). Reminder phone calls, texts, and/or emails will be sent to participants at their preferred contact method indicated on the Intake Form (Appendix B).

The Study Completion CRF (Appendix J) will be completed by a study team member to document the completion or withdrawal of all study participants.

Please see the Study Flow Diagram (Appendix L) for a visual representation of the study procedures.

Missed Appointments and Study Removal:

If a participant misses a scheduled appointment, they will be contacted to reschedule in order to maintain the treatment plan of their assigned study treatment group. In the event that a participant misses an appointment, study staff will make one attempt to reschedule each day on three separate days (for three total attempts to reschedule). If the participant cannot be reached or does not respond/reschedule, they will be removed from the study due to non-compliance.

Specimen Storage and Analysis:

All specimens will be collected, processed, and analyzed according to the recommendations of the respective manufacturer, current laboratory SOPs, or software recommendations. *When possible*, study staff will be blinded to treatment groups.

Molecular analyses will be performed over the following 6 months but may go on longer depending on the scope of assays performed, e.g. orthogonal validation.

Specimen Storage

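### Reserving a test group from about 92 participants gives very imprecise accuracy for the predictive models, and the splitting unit is not stated

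*Combined protocol and SAP*

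**What the plan says.** Section 11.1 (Statistical methods) allows tree-based methods, regression models and neural networks. For the networks, the number of layers and "other elements of model architecture will be determined empirically". The validation rule is one sentence: "Data will be split into training, cross validation, and testing groups in accordance with best practices" of the machine-learning and artificial-intelligence fields. It states no fractions, splitting unit or repetition. Bootstrap intervals are optional and are not tied to these models.

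Section 11.6 (Predictive Analytics) names one prediction target: the rate of, and time to, return to duty, with biomolecular signatures among the inputs.

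Section 11.2 plans "in order to evaluate a final sample of 92". Section 11.5 words this as "If we are able to enroll 150 participants (a minimum of 92 post-attrition".

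Section 10.1 takes blood and synovial fluid at baseline, and then "A follow-up blood draw and synovial fluid aspiration will be completed at 6 weeks". Each participant can therefore contribute two samples. Section 11.6 deals with repeated measures through random effects, but only in the multilevel models.

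**The concern.** Setting aside a test group is sound when data are plentiful. With about 92 people, the share set aside is too small to measure performance, and the people in it are lost to model fitting. A reported accuracy could then be compatible with anything from near chance to near perfect.

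The second issue is the undefined unit. If the two samples from one person were treated as separate rows and divided at random, a flexible model could recognise the person and return that person's outcome. Accuracy would then rise without any biological signal.

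What is at stake is whether a reader can interpret the accuracy reported for the return-to-duty models or any other predictive model from this trial.

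**Working it through.** **The plan's own figure.** The documents give no test-set size and no target precision, so there is none to reproduce. The 92 itself can be reproduced. Section 11.5 says "assuming an effect size of .2, we will achieve 90% power", with a significance threshold of .01. Reading .2 as f² in a regression F test with 2 numerator degrees of freedom, N = 92 and noncentrality 0.2 × 92 = 18.4, power is 0.9007, and 92 is the smallest N that reaches 90%. The 92 is therefore a fair base for the rest. It matches three groups (92/3 = 30.7, hence "a final sample of 92 (30-31 per arm"), whereas four arms are randomised (92/4 = 23).

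**Size of the test group** (fraction assumed, since none is stated).

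| Participants analysed | 10% | 20% | 30% |
|---|---|---|---|
| 92 | 9 | 18 | 28 |
| 120-124 (30-31 in each of four arms) | 12 | 24-25 | 36-37 |
| 150 | 15 | 30 | 45 |
| 200 | 20 | 40 | 60 |

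**Precision of an AUC (Hanley-McNeil).** With m and n people in the two outcome classes, Q1 = A/(2−A), Q2 = 2A²/(1+A), and

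Var = [A(1−A) + (m−1)(Q1−A²) + (n−1)(Q2−A²)] / (mn).

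At A = 0.75: A(1−A) = 0.1875, Q1−A² = 0.0375 and Q2−A² = 0.0804. Balanced classes are assumed.

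- 9 v 9: Var = (0.1875 + 8 × 0.0375 + 8 × 0.0804)/81 = 0.01396. SE 0.118, 95% half-width 0.23, interval about 0.52 to 0.98.
- 12 v 12: SE 0.102, half-width 0.20.
- 14 v 14: SE 0.094, half-width 0.18.
- 46 v 46: Var = (0.1875 + 45 × 0.0375 + 45 × 0.0804)/2116 = 0.00260. SE 0.051, half-width 0.10, interval about 0.65 to 0.85.

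The last line treats the 92 out-of-fold scores as independent. They come from overlapping training sets, so 0.10 is approximate.

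**Precision of a proportion correct.** 13 of 18 correct (72%) has an exact 95% interval of 47% to 90%. A coin-flip classifier scores 13 or more of 18 with probability 4.8%.

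**Hold-out against resampling.** A simulation used one row per person, 92 people, 20 features, ridge classification with a fixed penalty and 500 runs. On pure noise, the SD of estimated accuracy was 0.117 for one 18-person hold-out and 0.057 for 5-fold cross-validation repeated 10 times. With a moderate true signal the SDs were 0.115 and 0.049.

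**Sample-level splitting.** A second simulation used 92 people × 2 samples, an outcome fixed per person and unrelated to the features, an 80/20 split and 400 runs per setting. Under a sample-level split, a test sample has its partner in training with probability about 0.80 (147/183). Mean test accuracy on pure noise, for assumed within-person correlations of 0.3 to 0.7:

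| Features (assumed) | Ridge | 1-nearest-neighbour |
|---|---|---|
| 10 | 0.51-0.53 | 0.50-0.67 |
| 50 | 0.54-0.61 | 0.59-0.90 |
| 500 | 0.66-0.88 | about 0.90 |

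At zero correlation there was no inflation (0.49-0.50). Splitting by participant gave 0.48-0.50 in every setting.

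**The case against.** A reader might infer that the plan fixes a single split, that it will leak between training and test data, and that the trial's main goal is thereby compromised. The documents support none of these.

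- **A fixed split.** The text does not say that the split is made once. It names cross validation and binds itself to accepted practice in the field, which could be read to include resampling and grouping by participant.
- **Leakage.** It is not planned, only not excluded. It needs one row per sample, a person-level outcome and features correlated within person. The one named target, return to duty, is one outcome per participant and fits one row per participant. In that layout the leak cannot occur.
- **The trial's main goal.** Section 9.4 defines biomolecular signatures as DNA, RNA or protein levels, not classifier output. None of Aims 1 to 4 is predictive modelling, and Aims 1 and 2 use additive and multilevel models. Neural networks are optional.

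It is also fair to say that the 20% fraction is assumed, that 92 is a minimum, and that a test group of 24-25 would bring the half-width down to about 0.20.

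All of this stands, and it limits the point. It does not remove the precision problem. The sentence does provide for a separate testing group, and at these sample sizes any conventional fraction makes that group small. An appeal to best practice also does not tell a reader which unit was chosen before results were seen.

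**Conclusion.** The point holds as a low-cost improvement to exploratory modelling. At 92 analysed and an assumed 20% test group, the 95% half-width for an AUC of 0.75 is about 0.23, a little over twice the 0.10 or so available from scoring everyone out of fold. This rests on balanced outcome classes. Unequal classes would widen both figures.

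The test group for return to duty could be smaller still, because that outcome concerns active-duty participants. Section 10.1 lists 77 + 135 = 212 active-duty cases against 1927 + 1416 = 3343 dependents and retirees, about 6% of the total. The enrolment mix is not stated, so the reduction cannot be sized.

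Inflation from splitting by sample is conditional. It ranges from nil to severe depending on features and correlation that the documents do not give, and it is absent with one row per participant. The Aim 1 and Aim 2 treatment comparisons are unaffected.

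**What to change.** Replace the split sentence in section 11.1 with:

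> Predictive performance is estimated by repeated nested cross-validation with the participant as the splitting unit, so all samples from one participant stay in the same fold. Scaling, imputation, feature selection, dimension reduction and architecture tuning are refitted within each training fold. Out-of-fold performance (AUC for binary outcomes, R-squared for continuous outcomes, a censoring-appropriate concordance measure for time to return to duty) is reported with a participant-level bootstrap interval.

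The cost is SAP wording and more computing time. No extra participants, samples or assays are needed. The downside is that no single untouched test set remains, so any model put forward for use would still need validation in new participants.

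### Section 11.1 gives two outlier rules that do not fit together, and the looser one lets genuine values be dropped or replaced with no flagging rule, arm-blinding or primary result fixed

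*Combined protocol and SAP*

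**What the plan says.** Section 11.1 (Statistical Considerations) deals with outliers twice.

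- The opening text ties removal to error: "Outliers will be removed if determined to be erroneous based on relevant clinical expertise".
- The later Outliers paragraph ties handling to the type of test: "they may be excluded for parametric methods, however, they may be included when using non-parametric methods".
- The same paragraph adds a fallback with a condition, "If a non-parametric method cannot be used (e.g., none exist or they are not sufficiently interpretable". When that condition is met, "the outlier may be excluded or replaced with a more appropriate value (e.g., a randomly selected value, the median"; multiple imputation by chained equations is also listed.
- It ends with a safeguard: "Results with and without the outlier will be compared to determine whether its exclusion impacts conclusions".

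Neither place says what counts as an outlier, whether values are flagged within each arm or across all arms, or who decides and with what knowledge of treatment. In section 10.1 (Specimen Storage and Analysis), blinding of staff to treatment group is promised only where feasible and is not linked to outlier decisions.

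Other parts of the plan bear on the point. The Statistical methods text of section 11.1 sends data that fail the t-test's assumptions to Wilcoxon tests. Section 11.6 evaluates Aim 1 with generalized additive models of fractional change in biomarkers, lets the multilevel models use suitable distribution families, and names a two-tailed t-test among the methods for proteomic primary and secondary outcomes.

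**The concern.** An error criterion has little purpose if values that are not errors may also be removed. Two analysts following section 11.1 in good faith could build different analysis sets: one keeps every value not shown to be wrong, the other drops or overwrites genuine extremes because a parametric model is being fitted.

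Genuine extremes are foreseeable here. Section 10.1 provides for saline lavage after a dry tap, and the processing steps describe no correction for dilution. A lavage sample at one visit and neat fluid at the other could give an extreme fractional change with no assay or entry error.

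Testing edited data as if they were the observed data can understate the variance and shift the arm means. If the editing is done separately by arm, or chosen after results are seen, the false-positive rate can also exceed its nominal level. The biomarker comparisons are the ones exposed.

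**Working it through.** **1. The two rules side by side**

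| | Opening text of 11.1 | Outliers paragraph of 11.1 |
|---|---|---|
| Trigger | Judged erroneous | Type of statistical method |
| Finding of error needed | Yes | No |
| Actions | Remove | Exclude; as a fallback, exclude or replace (random value, median, imputation) |
| Definition of outlier | None | None |
| Flagging pooled or blind to arm | Not stated | Not stated |
| Primary result | Not stated | Not stated; with and without are compared |

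A genuine extreme value in a parametric analysis is not covered by the first rule and may be excluded under the second.

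**2. Why the flagging step matters**

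The two-arm statistic is t = (m1 − m2) / [s·√(1/n1 + 1/n2)], with s the pooled standard deviation of the data as analysed. If each arm is edited by its own cut-offs, s shrinks, but the edited means vary more between repeated trials than s implies, so |t| is too large too often. If flags and any replacement value come from the pooled data without using arm, the arm labels stay exchangeable under the null, so the test should stay close to its nominal level.

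**3. Inputs**

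- Level: "Hypothesis tests will be two-tailed and statistical significance will be considered at the putative threshold", given as 0.05 in section 11.6. For sample size, section 11.5 says "Significance threshold for power calculations was considered to be .01", so one case below is also shown at 1%.
- Arm size: section 11.2 gives 92 evaluable, 30–31 per arm. That fits three arms (92/3 = 30.7); the four randomised arms give 92/4 = 23. Both 23 and 31 were used.
- Assumed, because the documents give no figure: lognormal data with log-SD 0.5 to 1.2 (normal data for contrast), a pooled-variance t-test, and a 1.5-IQR flag rule.

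The plan gives no figure of its own for outlier handling to reproduce. The power figure in section 11.5 does not bear on this point.

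**4. Type I error with no true difference**

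Flags set within arm, 23 per arm, nominal 5%, 6,000 runs per cell (simulation standard error at 5%: √(0.05 × 0.95 / 6,000) = 0.28 percentage points):

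| Handling | log-SD 0.5 | 0.8 | 1.2 |
|---|---|---|---|
| Exclude | 12.4% | 15.8% | 19.8% |
| Median | 15.3% | 19.2% | 23.9% |
| Random value | 14.5% | 19.0% | 23.9% |

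Keeping all values gave 3.6–5.0%. Separate runs at 23 and 31 per arm gave about 12–20% for exclusion and 14–25% for the median. The random-value figure depends on which values may be drawn, which the plan does not say.

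Flags set within arm, 31 per arm, log-SD 1, 40,000 runs:

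| Nominal level | Keep | Exclude | Median | Random value |
|---|---|---|---|---|
| 5% | 4.2% | 18.9% | 22.6% | 22.2% |
| 1% | 0.5% | 6.8% | 9.7% | 9.3% |

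Exclusion thus gives 18.9/5 = 3.8 times the nominal 5% rate. Across other flag rules (3 IQR, 2 SD, 3 SD) and skewed shapes, including log-SD 1.5, the range at 31 per arm was 7.8–23.3% for exclusion and 8.2–28.2% for the median. The size therefore depends heavily on a rule that the plan does not give.

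Other readings, nominal 5%:

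| Reading | Type I error |
|---|---|
| Normal data, 1.5-IQR flags within arm | about 8–9% |
| Skewed data, pooled flags, one fixed handling | 4.9–5.6% |
| Skewed data, pooled flags, smallest p-value among keep, exclude and replace | about 8–9% |
| Skewed data, Wilcoxon on all values when a normality test fails, otherwise t-test | 4.5–6.0% |

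The second row needs one qualification. It holds for exclusion, or for a replacement taken from the pooled data. Replacing a pooled-flag outlier with its own arm's median brings arm back into the editing, and the rate then reaches up to 7.8%.

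**The case against.** The other side has a good case on size.

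- **Replacement is a fallback.** Median, random or imputed values apply only where no usable non-parametric method exists. A reader might infer that any outlier may be overwritten; the text does not say that. Exclusion, however, carries no condition beyond use of a parametric method, and the fallback extends to methods judged hard to interpret, which is a matter of opinion.
- **The plan has another route for skewed data.** With a Shapiro-Wilk check per arm at 0.05, 82–100% of skewed datasets went to Wilcoxon and the inflation largely disappeared. This stands for two-group tests. It is not a full answer: section 11.1 makes the normality check optional, about 6.5–8.6% remained with normal data and within-arm exclusion, and Aim 1 is a model, not a two-group test. The distribution families in section 11.6 help in the same way but are not required in place of exclusion.
- **Within-arm flagging is an assumption.** The documents never state it, and pooled flags with one fixed handling keep the error near 5%. This stands. It makes the inflation conditional, but the plan does not require the safe choice.
- **The with/without comparison is promised.** It is a real safeguard, but it does not say which result counts if the two disagree.
- **The two texts might be a general rule and its method-specific detail.** The opening text does not say that only errors may be removed. Conflict is the natural reading, not the only one. On either reading, genuine values may be excluded under undefined criteria.

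**Conclusion.** The point holds as an inconsistent and open-ended outlier rule. Section 11.1 permits genuine values to be excluded and, under a condition, replaced. It does not define an outlier, require arm-blind or pooled flagging, fix one handling, or name the primary result. P-values and confidence intervals can be wrong as a consequence.

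The size is conditional. At nominal 5% it is about 12–20% with exclusion and 14–25% with median replacement if skewed data are flagged within arm and tested with a t-test; about 8–9% with normal data flagged within arm, or with skewed data and a choice among handlings after seeing results; and near 5% with pooled flags and one fixed handling, or on the Wilcoxon route with skewed data. These figures rest on assumed lognormal data, assumed flag rules and the t-test.

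A reader might go further and infer that the plan will inflate false positives, or that the Aim 1 results will be wrong. The documents do not support that. They do not prescribe within-arm flagging, they offer rank tests and suitable distribution families, and the Aim 1 generalized additive model was not simulated. Skewness is not the whole cause either, since within-arm flagging also inflates error in normal data.

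**What to change.** Use one rule in both places in section 11.1:

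- Remove or correct a value only for a documented assay or entry error, decided blind to arm and recorded with the reason.
- Delete median and random-value replacement, and the option to exclude genuine values because a method is parametric.
- Name the analysis of all remaining values as primary, using a suitable transformation, distribution family, or robust or rank method, chosen in advance. A log scale is one valid option among these.
- Keep the with/without comparison as sensitivity only. State its flag rule and set the flags on pooled data.

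This changes SAP wording only and needs no new data. The downside is that estimates may be slightly less precise when genuine extremes stay in; a transformation or robust method can limit that loss.
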